4.12 Study Duration and Participant Time Commitments

The expected study duration for each participant will be approximately 5 years from the date of first sample collection (Table 1). We will do our best to minimize the number of on-site visits required by participants. Participants will have the option to provide research blood samples via their local community laboratory (e.g. LifeLabs or Dynacare). Result disclosure by the study team will be done over the phone, unless the participant is on-site for a clinical appointment, in which case results may be disclosed in person. Participants will be required to come into the hospital for diagnostic investigations done in follow-up to a “positive” cfDNA assay result.

Table 1. Participant requirements.

Activity	Year 1			Year 2			Year 3			Year 4			Year 5
Blood Collection ¹	x	x	x	x	x	x	x	x	x	x	x	x	
Test Results Returned to Participants (experimental cohort)	x	x	x	x	x	x	x	x	x	x	x	x	
Follow-up Diagnostic Investigations (experimental cohort)	Diagnostic investigations will ensue following a “positive” cfDNA assay result.												
Medical History and Demographic Questionnaire ²	x												
Patient-Outcome Questionnaire	x	x	x	x	x	x	x	x	x	x	x	x	
Collection of clinical data by study team.	Clinical data will be collected by the study team for up to 7 years from the date of study enrollment.												
Interviews (optional)	Interviews will be conducted over the course of the study. They will begin at the end of year 1.												

¹Tri-annual blood collection is only a study requirement for those randomized into the experimental cohort. Those in the control cohort have the option to provide up to 3 blood samples a year, ² The medical history questionnaire will be completed at least once by all participants at the time of study enrolment. Participants may be asked to update the questionnaire over the course of the study.

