5.0 Selection of Subjects

This study will enroll 1000 participants across Canada. Up to 1000 will be enrolled at UHN. Participants will be recruited from the genetics, surgical, medical, and radiation oncology clinics. If other sites join our study, the appropriate MTAs and DTAs will be established, and samples collected at other institutions (who have institutional REB approval for the study) will be sent to UHN for analysis. We are still in the process of determining which other sites will be involved in our study. Other sites may include: BC Cancer Agency, Mount Sinai Hospital, SickKids Hospital, Women’s College Hospital, Sunnybrook Hospital, McGill Research Institute, Jewish General Hospital, IWK Health Centre, Eastern Health. If the patient receives care at more than one of the above sites, their medical records from any of the other sites can also be looked at, regardless of which site they are enrolled at for this study.

5.1 Subject inclusion criteria.

Patients must fulfill the following criteria:

1. Patients with a confirmed diagnosis of HBOC, LS, NF1, LFS, PALB2, and HDGC (i.e., patients with an identified pathogenic variant in the respective cancer predisposition gene, or patients with uninformative genetic testing but with a family history suggestive of the cancer predisposition syndrome).
2. Patients must be receiving standard-of-care clinical assessment for cancer by a managing physician under a provincial screening program or cancer surveillance protocol.
3. All patients must have signed and dated an informed consent form for this study.

5.2 Subject exclusion criteria.

1. Patients must not have a personal history of cancer diagnosed and treated within 3 years prior to the expected first sample collection date for this study. If a patient has a personal history of cancer, treatment must have been completed successfully at least 3 years prior to first study sample collection.
2. Patients diagnosed more than 3 years prior to the expected first sample collection date, but never been treated for the cancer.
3. Patients undergoing investigations for a clinical suspicion of cancer.
4. Patients who are not able to comply with the protocol (i.e., tri-annual blood sample collection if randomized into the experimental cohort).

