5.3 Withdrawal of Subjects

If at any time a participant is found to be ineligible, as outlined in the inclusion and exclusion criteria, the participant will be removed from the study. In addition, if after obtaining informed consent the participant decides that they do not want to participate in the study, they may withdraw at any time at their own request. A participant may also be withdrawn from the study by the study team if not compliant with study requirements (e.g., completion of tri-annual blood collections if randomized into the experimental cohort).

If a participant is withdrawn from the study, the study team may continue to use the samples and corresponding data collected prior to withdrawal, unless the participant requests destruction of any samples not tested. Participant preferences will be documented by the study team. The study team will inform the participant that it is not possible to destroy samples and data which have already been processed and analyzed for research.

No study activities (including blood collections, questionnaires, data collection) will be completed for withdrawn participants. Any cfDNA test results received by the study team after a participant is withdrawn, will not be disclosed to the participant. Any diagnostic investigations following a positive cfDNA test result will not be initiated by the study investigator for withdrawn participants.

Withdrawn participants may be replaced by the study team, via the recruitment methods outlined above.

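### Section 5.3 allows withdrawal for missed blood draws, a requirement of the experimental arm only, which opens the randomised comparison to arm-specific loss of outcomes and selection

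*Protocol*

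**What the plan says.** Section 5.3 gives three ways out of the study. A participant found ineligible at any time is removed. A participant may leave at their own request. Thirdly, "A participant may also be withdrawn from the study by the study team if not compliant with study requirements", with one example: "e.g., completion of tri-annual blood collections if randomized into the experimental cohort".

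The consequences are the same for everyone withdrawn: "No study activities (including blood collections, questionnaires, data collection) will be completed for withdrawn participants", and "Withdrawn participants may be replaced by the study team, via the recruitment methods outlined above". Earlier material is not necessarily lost, because "the study team may continue to use the samples and corresponding data collected prior to withdrawal".

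The footnote to Table 1 in section 4.12 says that tri-annual "blood collection is only a study requirement for those randomized into the experimental cohort". Section 4.1 makes control-arm samples optional. Section 4.8.1 says that a missed questionnaire does not lead to removal. Section 4.10 says that the study is not blinded.

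On follow-up, section 4.1 commits the team to follow all participants for at least 5 years from first blood collection. Section 4.8 (Collection of Clinical Data) has clinical information recorded for all participants for up to 7 years from enrolment. Neither makes an exception for withdrawn participants. Section 8.0 then compares the cancer detection rate between the two cohorts of 500.

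**The concern.** Stopping the study test and leaving outcome follow-up are different events, and section 5.3 treats them as one. A participant in the experimental arm who misses draws can be taken out by staff who know the allocation. Any cancer diagnosed afterwards is then not recorded. A control has no blood schedule to miss.

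Two kinds of error could follow. Without replacement, cancers in the experimental arm go unobserved while the corresponding controls stay under observation. With replacement, people who missed draws give way to new recruits, and the arms are no longer the groups that randomisation formed. Whether those who miss draws differ in cancer risk is unknown. The plan itself treats drop-out by geography as worth examining: section 8.0 compares drop-outs from rural and remote regions across arms.

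The between-arm comparisons of detection, stage and time to diagnosis are at stake. Later analysis choices cannot restore outcomes that were never collected.

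**Working it through.** **1. The sections side by side**

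| Question | Experimental arm | Control arm |
|---|---|---|
| Is blood collection required? | Yes, tri-annually (4.12, Table 1 footnote) | No, optional (4.1) |
| Removed for a missed questionnaire? | No (4.8.1) | No (4.8.1) |
| Named example of non-compliance in 5.3 | Missed tri-annual draws | None |
| Own-request withdrawal, ineligibility removal | Yes (5.3) | Yes (5.3) |
| Data collected after withdrawal | None (5.3) | None (5.3) |
| Follow-up promised | At least 5 years (4.1); data up to 7 years (4.8) | Same |

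The arms differ in one row of substance: the non-compliance route has a named trigger in one arm only. The last two rows conflict with each other in both arms. The conflict is firmest with the 5-year minimum, since 7 years is an upper limit.

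**2. The plan's own figures**

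The protocol gives no withdrawal rate, so it has no figure on this point to reproduce. Section 8.0 claims more than 97% power for at least a 2-point increase from 5%. For 500 per arm and two-sided 0.05,

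power = Φ{[(p2 − p1) − 1.96·√(2·p̄(1 − p̄)/500)] / √[(p1(1 − p1) + p2(1 − p2))/500]}, where p̄ is the mean of p1 and p2.

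This gives 26.5% for 5% vs 7% and 85.2% for 5% vs 10%. The mismatch with the stated power is a separate matter. These values serve here only as a baseline.

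**3. Loss without replacement (assumed inputs)**

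Unobserved cancers = 500 × cancer rate × fraction withdrawn × fraction of follow-up lost. Assume 10% or 20% withdrawn, halfway through.

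- 5% rate: 500 × 0.05 × 0.10 × 0.5 = 1.25; with 20% withdrawn, 2.5.
- 7% rate: 500 × 0.07 × 0.10 × 0.5 = 1.75; with 20% withdrawn, 3.5.

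A 2-point effect is 500 × 0.02 = 10 cancers and a 5-point effect is 500 × 0.05 = 25. The range 1.25 to 3.5 is therefore 12.5% to 35% of the first and 5% to 14% of the second. If the experimental rate is itself 10%, the loss is 500 × 0.10 × 0.10 × 0.5 = 2.5, or 5 with 20% withdrawn.

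**4. Effect on power, same assumptions**

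Withdrawn people stay in the denominator. The observed experimental rate becomes p2 × (1 − w/2), where w is the fraction withdrawn.

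- w = 10%: 0.10 × 0.95 = 0.095, and power falls from 85.2% to 78.4%.
- w = 20%: 0.10 × 0.90 = 0.090, and power falls to 69.9%.

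The loss in steps 3 and 4 works against the cfDNA arm.

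**5. Selection with replacement (a different scenario, not to be added to step 3)**

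Suppose there is no true effect and the rate is 5% in both arms. In the experimental arm only, a fraction w is taken out of the analysis and replaced by people like those retained. Let r be the cancer risk of the withdrawn relative to the retained. The rate in the resulting arm is 0.05 / (1 − w + w·r).

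| w | r | Rate | Spurious difference | Two-sided rejection |
|---|---|---|---|---|
| 10% | 0.5 | 0.05/0.95 = 5.26% | +0.26 points | 5.4% |
| 10% | 1 | 5.00% | 0 | 5.0% |
| 10% | 3 | 0.05/1.20 = 4.17% | −0.83 points | 9.7% |
| 20% | 0.5 | 0.05/0.90 = 5.56% | +0.56 points | 6.8% |
| 20% | 1 | 5.00% | 0 | 5.0% |
| 20% | 3 | 0.05/1.40 = 3.57% | −1.43 points | 20.0% |

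The direction depends on r, and at r = 1 there is no bias. Taking the withdrawn out of the analysis altogether is an extreme case. Keeping their earlier data, as section 5.3 allows, would be expected to soften it.

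**The case against.** A reader might infer that randomisation is broken in one arm while controls face no rule at all. The documents do not support that.

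- The non-compliance sentence speaks of any participant, is permissive, and offers the blood draw as an example. It sets no number of missed draws.
- Own-request withdrawal, the end of data collection and replacement apply to both arms.
- Exclusion criterion 4 in section 5.2, "Patients who are not able to comply with the protocol (i.e., tri-annual blood sample collection if randomized into the experimental cohort", is put to everyone before allocation and so selects both arms alike. It becomes arm-specific only if it is read together with removal for ineligibility at any time. Read that way, inclusion criterion 2 (being under standard-of-care assessment) would equally remove a control who left surveillance, and section 7.0 has compliance with routine screening monitored without limit to one arm.

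A reader might also infer that the experimental arm becomes a per-protocol group and that every comparison is biased. That too goes beyond the text. Data from before withdrawal may be kept, so cancers found by then can count, and observed time can contribute to time to diagnosis. Nor can the lost cancers of step 3 be combined with replacement, because new recruits contribute cancers of their own.

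Finally, the analysis set is commonly left to the statistical analysis plan, which is not shown and may well specify analysis as randomised.

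These points limit the wording and the size, and they stand. The narrower point also stands: the only compliance requirement that section 5.3 names is one that no control can breach. An analysis plan can keep withdrawn people in the denominator, but it cannot supply outcomes that the protocol says will not be collected.

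**Conclusion.** The concern holds as a vulnerability written into the protocol. Section 5.3 adds a discretionary, unblinded route out of outcome follow-up that falls in practice on the experimental arm. It also contradicts the follow-up promised to all participants in sections 4.1 and 4.8. The comparison is open to arm-specific attrition and selection bias; bias is not certain.

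The size cannot be fixed from the documents. It depends on how many are withdrawn, when, at what cancer risk, and whether they are replaced. Under the assumed 10-20% withdrawn halfway, a 5-7% cancer rate and no replacement, 1.25 to 3.5 cancers go unobserved. With replacement, the assumed risk ratios of 0.5 to 3 give spurious differences from +0.56 to −1.43 points, and none when the risks are equal. The text should be corrected because the loss cannot be recovered once it has happened and the correction is cheap.

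**What to change.** Reconcile sections 4.1, 4.8 (Collection of Clinical Data) and 5.3 as follows.

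- State that missed blood draws do not by themselves end outcome follow-up. Whether and when draws or testing cease is a separate matter for the sponsor, and no rule is proposed here.
- Continue to collect cancer outcomes from records in both arms for the planned period, unless the participant withdraws consent for that collection.
- Do not replace participants after randomisation. Any extra recruits are additional randomised participants, and the original ones stay in their allocated arm for the between-arm comparison.
- Limit removal for ineligibility to facts that existed before randomisation, and report such removals by arm.

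The cost is a protocol amendment and a sentence in the consent form on continued record review. Record collection for up to 7 years is already planned. The statistical price is some dilution of the effect, because non-adherent participants remain in the experimental arm.

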11.9 Incidental Findings

Due to the nature of genomic sequencing, findings from this research (medically actionable variants) may have implications on the health of study participants or their family. In the event that a pathogenic germline variant is identified in a disease-relevant gene that may have implications for the health of the participant and his/her blood relatives, participants are asked to indicate whether they wish to be informed of such incidental germline findings. Alternatively, participants may indicate that they do not want to be told of clinically relevant incidental germline findings. For participants who wish to be informed, the study doctor or treating physician will contact the individual (or his/her specified delegate in the event that the patient is unwell or deceased), to inform him/her that a potentially clinically relevant incidental finding has been identified without disclosing the specific variant identified or its health implications. Participants will be offered the opportunity for rapid referral to a local medical genetics clinic (e.g. where the patient was first identified to have their HCS mutation), where a genetic counselor will review the medical, familial, and insurance considerations of disclosure of the incidental germline findings before the information is shared with the consenting patient or his/her delegate.

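### Section 5.3 withholds a late cfDNA positive, and study-started work-up of it, even from withdrawn participants who never declined the result (rare, minor)

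*Protocol*

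**What the plan says.** Section 5.3 describes how participants leave the study. They may leave at their own request. The team may also end participation: "A participant may also be withdrawn from the study by the study team if not compliant with study requirements". A separate sentence, beginning "If at any time a participant is found to be ineligible", says that ineligible participants are removed.

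Two rules then apply to withdrawn participants without qualification:

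- On disclosure: "Any cfDNA test results received by the study team after a participant is withdrawn, will not be disclosed to the participant".
- On work-up: "Any diagnostic investigations following a positive cfDNA test result will not be initiated by the study investigator for withdrawn participants".

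The section also says "Participant preferences will be documented by the study team", but that sentence closes a passage on keeping or destroying samples. Nothing there asks about a result still in the laboratory.

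Section 11.9 handles another kind of result differently. For incidental germline variants, "participants are asked to indicate whether they wish to be informed of such incidental germline findings". It also names who acts: "For participants who wish to be informed, the study doctor or treating physician will contact the individual".

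**The concern.** The two rules depend only on withdrawal status. They do not ask who ended participation or whether the participant wants the result. For someone who leaves by choice and wants no further contact, silence is reasonable. For someone withdrawn by the study team, or someone who leaves but would still want to know, the protocol gives no reason for it.

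The withheld item is more than a research signal. Section 4.4 describes the first-line assays as clinically validated, and Section 4.5 has a licensed geneticist sign out each report. Section 4.13.2 counts a diagnosis and treatment following a positive among the benefits of taking part. A carrier at high risk could therefore have a signed report of a cancer signal that the study does not pass on.

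The work-up rule reaches further than the disclosure rule. As worded, it also covers a positive that arrived before withdrawal but had not yet been investigated.

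**Working it through.** **No figure to reproduce.** This is a rule of conduct. The protocol states no withdrawal rate and no count of affected participants. The check has two parts: which routes stay open for a late positive, and how often one would occur.

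**Routes after withdrawal**

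| Route | Where | Status after withdrawal |
|---|---|---|
| Study team tells the participant | Section 4.6 | Barred by Section 5.3 |
| Study Doctor starts work-up | Section 4.6 | Barred by Section 5.3 |
| Managing physician acts on the result | Section 2.1 mentions results going to managing physicians | Not barred, but Sections 4.5 and 4.6 contain no step that sends it |
| Report uploaded to EPIC | Section 4.5 | Not stated |
| Copy at the participant's request | Section 4.6 | Not stated; the participant would have to ask |
| Usual surveillance | Sections 4.1 and 6.0 | Continues, independent of the cfDNA result |

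The two unclear rows arise because "No study activities (including blood collections, questionnaires, data collection) will be completed for withdrawn participants", and the text does not say whether upload or supplying a copy counts as a study activity.

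**Inputs from the protocol**

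- Experimental arm: 500 (Protocol Summary).
- Draws every four months for four years (Section 4.1): an interval of 365.25 / 3 = 121.75 days and 12 draws each.
- Target reporting time: 45 days from receipt at the laboratory (Section 4.5).
- Positives: up to about 5-10% of experimental participants per year (Section 6.0), an upper figure.
- Cancer detection: 5% to 10% by the end of the study (Section 8.0).

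**Assumptions**

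- Withdrawal of 5%, 10% or 20% over the trial.
- Timing of withdrawal unrelated to draws.
- A pending window of 45 days, or 59 days if 14 are added for transport and handling.

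**Step 1. Chance that a result is pending at withdrawal.** 45 / 121.75 = 0.370; 59 / 121.75 = 0.485.

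**Step 2. Chance of a positive per test.** 1 - (1 - 0.05)^(1/3) = 0.0170; 1 - (1 - 0.10)^(1/3) = 0.0345.

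**Step 3. Expected withheld positives** = 500 x withdrawal share x pending share x positives per test. For example, the lowest is 500 x 0.05 x 0.370 x 0.0170 = 0.16 and the highest is 500 x 0.20 x 0.485 x 0.0345 = 1.67.

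**Step 4. Expected true cancers among them.** 500 x 5% = 25 and 500 x 10% = 50 cancers, spread over 500 x 12 = 6,000 draws, give 0.42% to 0.83% per draw. This assumes that every cancer is cfDNA-positive, at one draw. The lowest is 25 x 0.370 x 0.0042 = 0.04 and the highest is 100 x 0.485 x 0.0083 = 0.40.

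| Withdrawal (assumed) | Withdrawn | Result pending | Withheld positives | Chance of at least one | True cancers |
|---|---|---|---|---|---|
| 5% | 25 | 9.2-12.1 | 0.16-0.42 | 15-34% | 0.04-0.10 |
| 10% | 50 | 18.5-24.2 | 0.31-0.84 | 27-57% | 0.08-0.20 |
| 20% | 100 | 37.0-48.5 | 0.63-1.67 | 47-81% | 0.15-0.40 |

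These counts cover all withdrawals, including people who left by choice. The protocol gives no split, so the smaller group who did not choose to leave cannot be sized from it. The counts also leave out positives received before withdrawal but not yet worked up.

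**The case against.** The strongest reply is that this is a deliberate boundary. Withdrawal ends the study's contact, a positive does not establish cancer (Section 4.6), and false positives lead to unnecessary procedures (Section 4.13.1). That justifies silence towards someone who wants no contact. It does not justify silence towards someone who was never asked.

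The second reply is that the group of most concern is very small. Section 5.3's own example of non-compliance is missed blood draws, and a participant who misses draws seldom has a sample in process. That withdrawal is also discretionary, so the team could wait for a pending report. Both arguments stand and lower the counts.

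Third, Section 11.9 is an imperfect model. It concerns germline variants that matter to relatives, and it does not say that it survives withdrawal. It shows only that the protocol already knows how to ask for a preference and name a contact.

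Fourth, the consent form is not among the documents and may cover pending results. No claim is made about it.

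Three stronger readings are tempting but unsupported:

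- A reader might infer that no one may act on a late positive. Section 5.3 bars disclosure to the participant and work-up started by the study investigator. It does not bar the managing physician, and Section 2.1 gives that physician a follow-up role. What is absent is the step that delivers the result.
- A reader might infer that the rules plainly cover participants found ineligible. The text calls them removed, not withdrawn, so this is only an inference from the section heading.
- A reader might infer a contradiction with the return of results in Section 4.6. Section 5.3 is a specific rule for withdrawn participants and can stand beside the general one.

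**Conclusion.** The point holds as a minor participant-safety matter. Section 5.3 is fixed more broadly than its likely purpose requires, because it treats a participant who has not declined a result like one who has. With assumed withdrawal of 5-20%, roughly 0 to 2 positives would be withheld over the trial across all withdrawals, and well under one of them is expected to be a true cancer. The number among people who did not leave by choice is smaller.

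The size rests on a withdrawal rate that the protocol does not give, on a positive rate stated as an upper figure, and on withdrawal being unrelated to the timing of draws. The event is rare but foreseeable, since a result is in process for more than a third of each draw interval.

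There is no effect on power or on the primary comparison. The protocol collects no further study data on withdrawn participants whether or not a late result is disclosed.

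**What to change.** In Section 5.3:

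1. Extend the preference documented at withdrawal to cfDNA results that are still pending.
2. Unless the participant declines, disclose a positive that is pending or not yet worked up, and hand it to the managing physician for work-up. This should apply whoever ended participation.

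The cost is one field on the withdrawal form, a few sentences of protocol text and research ethics board approval of the wording. The field may partly repeat the consent form. The downside is occasional contact with a withdrawn participant who did not decline; anyone who does decline is left alone, as now.
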